10.5 Other Required Reporting

10.5.1 Unanticipated Problems Involving Risks to Subjects or Others (UPIRTSOS) in general, include any incident, experience, or outcome that meets all of the following criteria:

1. Unexpected (in terms of nature, severity, or frequency) given (a) the research procedures that are described in the protocol-related documents, such as the IRB-approved research protocol and informed consent document; and (b) the characteristics of the subject population being studied;
2. Related or possibly related to participation in the research (in this guidance document, possibly related means there is a reasonable possibility that the incident, experience, or outcome may have been caused by the procedures involved in the research); and
3. Suggests that the research places subjects or others at a greater risk of harm (including physical, psychological, economic, or social harm) than was previously known or recognized.

Some unanticipated problems involve social or economic harm instead of the physical or psychological harm associated with adverse events. In other cases, unanticipated problems place subjects or others at increased *risk* of harm, but no harm occurs.

Note: If there is no language in the protocol indicating that pregnancy is not considered an adverse experience for this trial, and if the consent form does not indicate that subjects should not get pregnant/impregnate others, then any

pregnancy in a subject/patient or a male patient's partner (spontaneously reported) which occurs during the study or within 120 days of completing the study should be reported as a UPIRTSO.

If the event meets the criteria for an UPIRTSO, submit to your IRB as required by your institutional policies.

10.52 Adverse events to be graded at each evaluation and pretreatment symptoms/conditions to be evaluated at baseline per the CTCAE v5.0 grading unless otherwise stated in the table below:

System Organ Class (SOC)	Adverse event/Symptoms	Baseline	Each evaluation
Gastrointestinal disorders	Diarrhea	# stools per day	X
	Nausea	X	X
	Vomiting	X	X
General Disorders	Fatigue	X	X
	Palmar-plantar erythrodysesthesia syndrome	X	X
Skin and Subcutaneous Tissue Disorders	Rash maculo-papular	X	X
Vascular disorders	Hypertension	X	X
Investigations	Blood bilirubin increased	X	X
	Alanine aminotransferase increased	X	X
	Aspartate aminotransferase increased	X	X

10.53 Submit via appropriate Academic and Community Cancer Research United (ACCRU) Case Report Forms (i.e., paper or electronic, as applicable) the following AEs experienced by a patient and not specified in Section 10.5:

10.531 Grade 2 AEs deemed *possibly, probably, or definitely* related to the study treatment or procedure.

10.532 Grade 3 and 4 AEs regardless of attribution to the study treatment or procedure.

10.533 Grade 5 AEs (Deaths)

10.5331 Any death within 30 days of the patient's last study treatment or procedure regardless of attribution to the study treatment or procedure.

10.5332 Any death more than 30 days after the patient's last study treatment or procedure that is felt to be at least possibly treatment related must also be submitted as a Grade 5 AE, with a CTCAE type and attribution assigned.

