1.3 Anti-EGFR antibody-related adverse events

EGFR may control proliferation and differentiation of keratinocytes in normal skin. Inhibition of EGFR results in cessation of proliferation and migration of keratinocytes, leading to apoptosis. In addition, inflammatory cytokines are released, and the entire epidermis may become thin, fragile, vulnerable, and unable to retain moisture¹⁶. Rash acneiform is the most common skin disorder, and usually occurs within 1 to 3 weeks after administration of an anti-EGFR antibody. The most commonly affected area is the upper trunk, including the face, anterior chest, back, and forearm. The severe rash acneiform is often associated with itching and pain. It is replaced by skin dryness and cracking approximately 4 weeks after administration. Paronychia characterized by impaired nail growth and periungual pain may occur 8 weeks or later and be complicated by granulation or abscess in serious cases^{16,17}. Grade 3 or higher skin toxicity has been reported in 9.4% to 16.7% of patients treated with cetuximab⁵⁻⁸, partly contributing to

premature discontinuation of treatment. Another significant adverse drug reaction is severe infusion reaction, with an incidence of less than 5% and interstitial pneumonia (1-2%). In addition, hypomagnesemia, hypokalemia, and hypocalcemia have been reported, requiring monitoring of serum electrolytes before, during, and after treatment and appropriate supplementation as needed.

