1.5 Regorafenib-related adverse events

In the CORRECT study, the common grade 3 or higher adverse events related to regorafenib were hand- foot-skin reaction (16.6%), fatigue (9.6%), hypertension (7.2%), diarrhea (7.2%), and rash/exfoliation (5.8%). Drug-related adverse events led to discontinuation of treatment in 8.2% in the regorafenib group and 1.2% in the placebo group¹⁹. It has been reported that adverse events, primarily hand- -foot-skin-reaction, occurred the most frequently in the first course, and the incidence decreased thereafter due to appropriate dose reduction²¹.

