Safety Population: The Safety Population comprises all patients who received any protocol treatment.

- 16.11 **Primary Endpoint:** The primary endpoint is overall survival. The primary objective for this trial is to compare the overall survival (OS) between evaluable patients who were randomized to arm A and arm B. Overall survival is defined as the time from randomization to death from any cause. Patients who are alive at the time of statistical analysis will be censored at the last known alive date.
- 16.12 **Secondary Endpoints:** Each secondary endpoint will be compared between arms. These include first progression free survival (PFS1), second progression free survival two (PFS2), sequential treatment progression free survival (stPFS), objective response rate of initial treatment and sequential treatment, and incidence of adverse events from initial treatment, sequential treatment and whole period.

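### The solicited adverse-event table in 10.52 covers regorafenib's signature toxicities but not those of anti-EGFR therapy, so any-grade summaries would mix two capture rules

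*Combined protocol and SAP*

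**What the plan says.** Section 10.52 sets out a table of "Adverse events to be graded at each evaluation and pretreatment symptoms/conditions to be evaluated at baseline per the CTCAE v5.0 grading". It has ten terms: diarrhea, nausea, vomiting, fatigue, "Palmar-plantar erythrodysesthesia syndrome", "Rash maculo-papular", hypertension, and increases in bilirubin, ALT and AST.

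Section 10.53 governs events outside that table. (It refers to events not specified in Section 10.5, which I read as 10.52.) Grade 2 events are submitted if at least possibly related. Above that, the rule covers "Grade 3 and 4 AEs regardless of attribution to the study treatment or procedure". Grade 5 events have their own rule. Nothing is required for grade 1.

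On the comparison, goal 2.24 addresses frequency and severity of adverse events between the arms. Section 16.12 compares "incidence of adverse events from initial treatment, sequential treatment and whole period". Section 16.326 plans a summary by frequency and severity under CTCAE v5.0. It gives no grade threshold and does not separate solicited from unsolicited terms.

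On expected toxicity, section 1.3 states for anti-EGFR antibodies that "Rash acneiform is the most common skin disorder" and also names hypomagnesemia. Section 10.31 lists acneiform rash and maculo-papular rash as separate terms, so the maculo-papular row does not stand in for acneiform rash.

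**The concern.** Section 1.9 justifies the trial partly by the different toxicity profiles of the two regimens, so the low-grade safety picture is part of what a reader will want from it. If one regimen's characteristic events are asked about at every visit and graded at baseline, while the other's are recorded only above a threshold, the any-grade profile partly reflects the form and not the drugs.

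The missing baseline grade matters as well, because incidence by period needs a starting point. Section 1.3 says paronychia may appear 8 weeks or later. An arm B patient may therefore carry low-grade skin toxicity into sequential regorafenib with no required grade at the switch. Section 18.1 provides a sequential-treatment baseline form for RECIST measurements but none for adverse events.

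**Working it through.** No figure in the plan is at issue here. The check compares texts and adds one illustration under stated assumptions.

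**Step 1: toxicities the protocol names, against the 10.52 rows.**

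| Source | Toxicity | Row in 10.52? |
|---|---|---|
| 1.5, regorafenib, grade 3+ | Hand-foot skin reaction (16.6%) | Yes |
| | Fatigue (9.6%) | Yes |
| | Hypertension (7.2%) | Yes |
| | Diarrhea (7.2%) | Yes |
| | Rash/exfoliation (5.8%) | Yes (maculo-papular) |
| 1.3, anti-EGFR | Acneiform rash | No |
| | Skin dryness, paronychia | No |
| | Low magnesium, potassium, calcium | No |
| | Infusion reaction, interstitial pneumonia | No |
| 15.47, irinotecan boxed warnings | Severe diarrhea | Yes |
| | Severe myelosuppression | No |

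All five leading regorafenib toxicities have a row. None of the events that 1.3 names for anti-EGFR antibodies does.

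**Step 2: what must be recorded.**

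| | Listed in 10.52 | Not listed (10.53) |
|---|---|---|
| Baseline grade | Required | Not required |
| Grade 1 | Recorded | Not required |
| Grade 2, at least possibly related | Recorded | Recorded |
| Grade 2, unlikely or unrelated | Recorded | Not required |
| Grade 3 or 4 | Recorded | Recorded |

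The formal gap is grade 1, plus grade 2 judged unlikely related or unrelated. Acneiform rash during anti-EGFR treatment will seldom be judged unrelated, so for that term the gap is essentially grade 1 and the baseline grade.

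**Step 3: direction and possible size.** These inputs are assumptions, not document figures. Each regimen has one signature toxicity with the same true rate g of patients whose worst grade is 1. It is recorded for regorafenib and not for anti-EGFR. A share c of each arm starts sequential treatment. The two terms are counted additively. The true difference between arms over the whole period is then zero. The recorded differences, arm A minus arm B, are:

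- Initial phase: g − 0 = +g
- Sequential phase, among those who start it: 0 − g = −g
- Whole period: g − c·g = (1 − c)·g

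| g | Initial | Sequential | Whole, c = 50% | Whole, c = 70% | Whole, c = 100% |
|---|---|---|---|---|---|
| 20% | +20 points | −20 | +10 | +6 | 0 |
| 30% | +30 | −30 | +15 | +9 | 0 |
| 40% | +40 | −40 | +20 | +12 | 0 |

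Full cancellation needs c = 100%. Sections 13.5 and 13.6 leave the move to sequential treatment to the physician, so c will probably be lower.

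**Step 4: what is untouched.** Grade 3+ events have the same capture rule for all terms. The stopping rule in 16.42 uses grade 4 or higher. The primary analysis is of overall survival.

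**The case against.** The strongest reply is that capture differs by term, not by arm. Acneiform rash is recorded by the same rule in arm A and arm B, and so is every other term. A term-by-term table therefore contains no arm-dependent rule, and 16.326 does not announce any pooling of terms. This stands. What remains is that the any-grade acneiform rash row is under-counted, and that any pooled count or contrast between unlike terms sets one capture rule against another. Section 16.326 does not rule such summaries out. A patient with grade 1 acneiform rash who also has a solicited event still counts in an any-event total, which further limits the effect there.

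Existing capture also helps. Blood counts and magnesium are scheduled in both test tables (4.1 and 4.2), and 18.1 requires laboratory forms at baseline and each evaluation. If those forms hold these values, low-grade neutropenia and hypomagnesemia could be graded afterwards. The form contents are not shown, and acneiform rash has no such fallback. Section 10.31 says its listed events, including any-grade acneiform rash and hypomagnesemia, must still be routinely reported. It refers that reporting to 10.53, which has no route for grade 1.

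Four stronger readings are tempting, and the documents do not support them:

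- *That irinotecan's main toxicities are left out.* Diarrhea, nausea and vomiting are solicited; the clear omission is neutropenia.
- *That only anti-EGFR events are lost.* Section 15.17 lists common regorafenib events that are also unsolicited, such as mucositis, proteinuria and neutropenia. The imbalance concerns signature toxicities.
- *That the comparison is biased against one arm throughout.* Step 3 shows that the sign reverses in the sequential phase.
- *That a definite number of arm B patients goes missing.* No grade 1 rate for acneiform rash is given. Applying an assumed rate to 26 per arm would also use the wrong denominator: 26 is the evaluable target for survival, whereas the Safety Population is everyone treated.

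**Conclusion.** The point holds in limited form. The solicited list is lopsided in signature toxicities, and 10.53 leaves a gap that is mainly grade 1 events and baseline status for the unlisted terms. Any-grade summaries that pool or contrast terms would favor anti-EGFR therapy over regorafenib as a drug. That works against arm A in the initial phase and against arm B in the sequential phase, with partial cancellation over the whole period.

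The size cannot be derived from the documents. The 20 to 40 points for the initial phase rest wholly on assumed, equal grade-1-only rates and on complete non-recording of the unlisted term. Sites may volunteer some grade 1 events, which would shrink the difference. Safety is a secondary endpoint with no test specified in 16.326 and no part in the decision rule in 16.23. This is an inexpensive improvement to a stated secondary comparison and does not threaten the trial's main conclusion.

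**What to change.** Add rash acneiform, hypomagnesemia and neutrophil count decreased to the 10.52 table. Grade them at baseline and at each evaluation, in both arms and both treatment phases, and include a grade on entry to sequential treatment. Infusion-related reaction may be added too; it needs no baseline grade and applies only to anti-EGFR infusions.

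If the form cannot change, state in 16.326 that between-arm comparisons which pool or contrast different terms are restricted to uniformly captured grades, that is grade 3 and higher. Correct the reference in 10.53 to 10.52 at the same time, if that is what is meant.

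The cost is a few rows of data entry. Section 8.41 already requires skin symptoms to be graded before anti-EGFR dosing, and the laboratory terms can be graded from blood tests already scheduled. For patients already enrolled, low-grade and baseline data may not be recoverable. They include the 12 with left-sided tumors entered before Amendment 2, who belong to the Safety Population if treated. The report should say which patients were recorded under which version of the table.

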11.0 Treatment Evaluation Using RECIST Guideline

NOTE: This study uses protocol RECIST v1.1 template dated 2/16/2011. See the footnote for the table regarding measurable disease in Section 11.44, as it pertains to data collection and analysis.

Response and progression will be evaluated in this study using the new international criteria proposed by the revised Response Evaluation Criteria in Solid Tumors (RECIST) guidelines (version 1.1)³³. Changes in the largest diameter (unidimensional measurement) of the tumor lesions and the short axis measurements in the case of lymph nodes are used in the RECIST guideline.

11.1 Schedule of Evaluations: For the purposes of this study, patients should be reevaluated every 8 weeks.

11.2 Definitions of Measurable and Non-Measurable Disease

11.21 Measurable Disease

11.211 A non-nodal lesion is considered measurable if its longest diameter can be accurately measured as ≥ 1.0 cm with CT scan, CT component of a PET/CT, or MRI.

11.212 A superficial non-nodal lesion is measurable if its longest diameter is ≥ 1.0 cm in diameter as assessed using calipers (e.g. skin nodules) or imaging. In the case of skin lesions, documentation by color photography, including a ruler to estimate the size of the lesion, is recommended.

11.213 A malignant lymph node is considered measurable if its short axis is ≥ 1.5 cm when assessed by CT scan (CT scan slice thickness recommended to be no greater than 5 mm).

11.22 Non-Measurable Disease

11.221 All other lesions (or sites of disease) are considered non-measurable disease, including pathological nodes (those with a short axis ≥ 1.0 to <1.5 cm). Bone lesions, leptomeningeal disease, ascites, pleural/pericardial effusions, lymphangitis cutis/pulmonis, inflammatory breast disease, and abdominal masses (not followed by CT or MRI), are considered as non-measurable as well.

Note: 'Cystic lesions' thought to represent cystic metastases can be considered as measurable lesions, if they meet the definition of measurability described above. However, if non-cystic lesions are present in the same patient, these are preferred for selection as target lesions. In addition, lymph nodes that have a short axis <1.0 cm are considered non pathological (i.e., normal) and should not be recorded or followed.

11.3 Guidelines for Evaluation of Measurable Disease

11.31 Measurement Methods:

- All measurements should be recorded in metric notation (i.e., decimal fractions of centimeters) using a ruler or calipers.
- The same method of assessment and the same technique must be used to

characterize each identified and reported lesion at baseline and during follow-up. For patients having only lesions measuring at least 1 cm to less than 2 cm must use CT imaging for both pre- and post-treatment tumor assessments.

- Imaging-based evaluation is preferred to evaluation by clinical examination when both methods have been used at the same evaluation to assess the antitumor effect of a treatment.

11.32

Acceptable Modalities for Measurable Disease:

- Conventional CT and MRI: This guideline has defined measurability of lesions on CT scan based on the assumption that CT slice thickness is 5 mm or less. If CT scans have slice thickness greater than 5 mm, the minimum size for a measurable lesion should be twice the slice thickness.
- As with CT, if an MRI is performed, the technical specifications of the scanning sequences used should be optimized for the evaluation of the type and site of disease. The lesions should be measured on the same pulse sequence. Ideally, the same type of scanner should be used and the image acquisition protocol should be followed as closely as possible to prior scans. Body scans should be performed with breath-hold scanning techniques, if possible.

11.33

Measurement at Follow-up Evaluation:

- In the case of stable disease (SD), follow-up measurements must have met the SD criteria at least once after study entry at a minimum interval of 8 weeks (see Section 11.44).
- The cytological confirmation of the neoplastic origin of any effusion that appears or worsens during treatment when the measurable tumor has met criteria for response or stable disease is mandatory to differentiate between response or stable disease (an effusion may be a side effect of the treatment) and progressive disease.
- Cytologic and histologic techniques can be used to differentiate between PR and CR in rare cases (e.g., residual lesions in tumor types such as germ cell tumors, where known residual benign tumors can remain.)

11.4 Measurement of Effect

11.41 Target Lesions & Target Lymph Nodes

- Measurable lesions (as defined in Section 11.21) up to a maximum of 5 lesions representative of all involved organs, should be identified as “Target Lesions” and recorded and measured at baseline. These lesions can be non-nodal or nodal (as defined in 11.21), where no more than 2 lesions are from the same organ and no more than 2 malignant nodal lesions are selected.

Note: If fewer than 5 target lesions and target lymph nodes are identified (as there often will be), there is no reason to perform additional studies beyond those specified in the protocol to discover new lesions.

- Target lesions and target lymph nodes should be selected on the basis of their size, be representative of all involved sites of disease, but in addition should be those that lend themselves to reproducible repeated measurements. It may be the case that, on occasion, the largest lesion (or malignant lymph node) does not lend itself to reproducible measurements in which circumstance the next largest lesion (or

malignant lymph node) which can be measured reproducibly should be selected.

- Baseline Sum of Dimensions (BSD): A sum of the longest diameter for all target lesions plus the sum of the short axis of all the target lymph nodes will be calculated and reported as the baseline sum of dimensions (BSD). The BSD will be used as reference to further characterize any objective tumor response in the measurable dimension of the disease.
- Post-Baseline Sum of the Dimensions (PBSD): A sum of the longest diameter for all target lesions plus the sum of the short axis of all the target lymph nodes will be calculated and reported as the post-baseline sum of dimensions (PBSD). If the radiologist is able to provide an actual measure for the target lesion (or target lymph node), that should be recorded, even if it is below 0.5 cm. If the target lesion (or target lymph node) is believed to be present and is faintly seen but too small to measure, a default value of 0.5 cm should be assigned. If it is the opinion of the radiologist that the target lesion or target lymph node has likely disappeared, the measurement should be recorded as 0 cm.
- The minimum sum of the dimensions (MSD) is the minimum of the BSD and the PBSD.

11.42 Non-Target Lesions & Non-Target Lymph Nodes

Non-measurable sites of disease (Section 11.22) are classified as non-target lesions or non-target lymph nodes and should also be recorded at baseline. These lesions and lymph nodes should be followed in accord with 11.433.

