 - b. Unequivocal progression of existing non-target lesions and non-target lymph nodes. (NOTE: Unequivocal progression should not normally trump target lesion and target lymph node status. It must be representative of overall disease status change.)

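### Measurable lesions and nodes left over after the target cap have no class in Section 11.42, so sites may score the same scan differently for PFS1, PFS2, stPFS and response.

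*Combined protocol and SAP*

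**What the plan says.** All of this is in Section 11 of the combined protocol and SAP.

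- **11.21** defines measurability by size. It begins "A non-nodal lesion is considered measurable if its longest diameter can be accurately measured as" and sets 1.0 cm for non-nodal lesions; nodes need a short axis of at least 1.5 cm. Selection as a target plays no part.
- **11.22** covers the remainder: "All other lesions (or sites of disease) are considered non-measurable disease, including pathological nodes" with a short axis from 1.0 to below 1.5 cm, plus listed types such as bone lesions and effusions. Nodes below 1.0 cm are treated as normal and are not to be recorded.
- **11.41** limits targets: "up to a maximum of 5 lesions representative of all involved organs", and "no more than 2 lesions are from the same organ and no more than 2 malignant nodal lesions are selected".
- **11.42** defines the other class: "Non-measurable sites of disease (Section 11.22) are classified as non-target lesions or non-target lymph nodes and should also be recorded at baseline". These are then followed under 11.433.
- **11.432 and 11.433** score progression from the target sum, from new lesions, and from "Unequivocal progression of existing non-target lesions and non-target lymph nodes". A note to the last rule says that it should reflect a change in overall disease status and should not normally override the target result.
- **11.44** builds the overall status from target, non-target and new disease. There is no fourth class.

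Section 11.0 names RECIST 1.1 as the criteria for the study and says that a dated protocol template of it is used. Sections 16.321 and 16.322 determine progression by RECIST 1.1, and 16.323 says that the stPFS analysis follows the other PFS endpoints.

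**The concern.** A third measurable liver metastasis at baseline is not a target, because of the cap. It is not non-target, because it is measurable. It is not new, because it was there at the start. The same holds for a third node of at least 1.5 cm. It also holds for a lesion passed over under 11.41 because it cannot be measured reproducibly, if it still meets 11.21.

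A site that applies 11.42 as written leaves such lesions out of the status. A site that treats them as non-target can call PD on the same images. Progression is confirmed locally (6.41), and no central review is described that would reconcile the two.

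At stake are the progression dates for PFS1, PFS2 and stPFS and, where PD goes unscored, best response in 16.324 and 16.325. There is also a censoring route. Section 13.6 lets a patient move to sequential treatment for reasons other than PD, and 16.321 then censors PFS1 at the last assessment before that treatment. A real progression scored SD could thus become a censoring that is related to outcome.

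**Working it through.** The plan states no figure on this point, so the check is to trace the definitions, apply the scoring rules to constructed cases, and then see what a simulation can and cannot say.

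**Step 1. Trace the classes.** A baseline non-nodal lesion of at least 1.0 cm that 11.41 does not select:

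| Class | Source | Does it qualify? |
|---|---|---|
| Target | 11.41 | No, over the cap |
| Non-target | 11.42, non-measurable sites of 11.22 only | No, it meets 11.21 |
| New | 11.432, 11.433 | No, present at baseline |

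**Step 2. Apply 11.43 and 11.44 to a constructed patient.** Five measurable liver lesions and no other disease. Two are targets (3.0 + 2.5 = 5.5 cm) and three are unselected (3 × 2.0 = 6.0 cm), 11.5 cm in total.

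- *Case A: targets unchanged, each unselected lesion grows from 2.0 to 4.0 cm.* Target change is 5.5 / 5.5 − 1 = 0%. Total diameter is 5.5 + 12.0 = 17.5 cm, and 17.5 / 11.5 − 1 = 52%. Literal status: SD. With the unselected lesions as non-target: PD, if the growth is judged unequivocal.
- *Case B: targets disappear, unselected lesions stay at 2.0 cm.* Literal status: CR. With the unselected lesions as non-target: target CR with non-target Non-CR/Non-PD, which 11.44 scores PR.
- *Case C: targets shrink by 30% (5.5 × 0.70 = 3.85 cm), unselected lesions double as in A.* Total diameter is 3.85 + 12.0 = 15.85 cm, above the baseline 11.5 cm. Literal status: PR. With the unselected lesions as non-target: PD, if unequivocal.

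**Step 3. Which endpoints move?** Case A moves a progression date. Case B moves none: 16.324 and 16.325 count CR and PR alike. Case C moves both the progression date and the response. OS (16.11, 16.23) uses deaths only and does not depend on lesion class.

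**Step 4. Illustrative size.** Every input here is an assumption; none is in the documents. Four liver lesions, diameters lognormal with median 2.5 cm and log-SD 0.4, the two largest as targets. Eight-week log-growth has mean 0.1, patient-level SD 0.2, and lesion-level SD 0.1, 0.2 or 0.3. Target PD is the 11.432 rule (sum up at least 20% and 0.5 cm). A missed progression is taken as the unselected sum up at least 40% and 1 cm without target PD. That threshold is also assumed. The runs used 100,000 patients per setting; a repeat with 400,000 agreed to within 0.2 percentage points.

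| Lesion-level SD | Target PD | Missed | Missed / (missed + target PD) | Of the missed, target PD at next 8-week scan |
|---|---|---|---|---|
| 0.1 | 35.3% | 0.44% | 0.44 / 35.74 = 1.2% | 90% |
| 0.2 | 38.3% | 3.70% | 3.70 / 42.00 = 8.8% | 55% |
| 0.3 | 41.8% | 7.77% | 7.77 / 49.57 = 15.7% | 39% |

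The last column comes from the repeat run and assumes that each lesion keeps its growth rate. In the 0.3 setting, 36% of the missed cases have total diameter across all four lesions up by less than 20%. Under the 11.433 note many of those might not be called unequivocal progression even with the lesions classified.

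**The case against.** The strongest reply is that Section 11 is a local summary and RECIST 1.1 governs. Sections 11.0, 16.321 and 16.322 name it, and 8.44 uses it to define progression on anti-EGFR therapy, so a site can go to the guideline for the missing class. This stands in part. It rules out a reading that a reader might take from 11.42, namely that growth in these lesions can never be scored as progression. It does not close the gap, because Section 11.0 and the footnote in 11.44 tie data collection and analysis to the protocol's own template, and that template is silent. How the guideline classes such lesions cannot be checked from these documents.

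Four further points are fair.

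- **Other routes exist.** Section 11.45 allows PD for symptomatic deterioration, 8.3 and 8.44 list worsening symptoms or findings as grounds for stopping, and 6.41 and 13.6 allow re-registration for intolerance or other non-PD reasons. The inference that patients are locked out of the second sequence is not supported. These routes do not, however, classify the lesions.
- **Selection softens the effect.** Targets are chosen by size and to represent all involved sites, so unselected lesions often behave like them. The 0.1 row shows this.
- **The CR consequence changes no planned endpoint.** It is a misclassification, and it does not inflate the response rate.
- **The rule is the same in both arms,** and 16.32 attaches no significance level or decision rule to the affected endpoints.

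**Conclusion.** The gap in the written rules is real and follows from 11.21, 11.22, 11.41 and 11.42 without any assumption. Its realistic consequence is inconsistent local scoring of secondary endpoints: progression dates for PFS1, PFS2 and stPFS, and best response where PD is missed. The primary endpoint, its 42 deaths and its decision rule are untouched. It should be corrected, but the primary conclusion does not rest on it.

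The size is unknown. The documents do not give the share of patients with surplus measurable lesions or how such lesions grow. Under the assumed inputs, about 1 to 16% of progressions in such patients would be missed at a given scan. A reader might carry away the upper end, about 1 in 6. That is the most extreme setting, it uses a threshold that the protocol does not contain, and it counts as missed many progressions that the targets would show one scan later. Because 11.433 requires unequivocal progression that represents overall disease status, the true figure would be lower than the simulated one for the same growth pattern.

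**What to change.** Replace the first sentence of 11.42 with:

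> All malignant lesions and pathological lymph nodes (short axis at least 1.0 cm) not selected as targets under 11.41, whether measurable or non-measurable (11.22), are classified as non-target, recorded at baseline and followed per 11.433.

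The 1.0 cm limit is needed so that the sentence does not sweep in nodes that 11.22 says should not be recorded. Use the same wording for the Sequential Treatment (Baseline) RECIST form in 18.1, so that PFS2 and the sequential response rate start from the same classes.

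The cost is a few more baseline entries per patient. The scans are already taken, no visit is added, and no treatment rule changes. The scoring rules in 11.43 and the table in 11.44 can stay as they are.
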